5. STUDY CONDUCT

5.1 Schedule of Events for Diabetic Foot Ulcer (DFU) Patients:

Requirement	Run-In Period		Treatment Period (1) Week 0 is the initial application of study product and occurs 14 to 17 days after the start of the run-in period. Visit window for Weeks 1 through 12 is (± 3 days)												Two-Week In-Person Follow-Up (2)	Six-Month Telephone Follow-Up (2)	
	Start	7 days (± 3 days)	0	1	2	3	4	5 (3)	6	7	8	9 (3)	10	11	12	2 weeks after each wound closure (± 3 days)	Six-Months After Week 0 (± 1 month)
Informed consent	X																
Screening	X	X	X														
Demographics and history	X																
HbA1c	X(4)																
Vascularization (ABI, TBI or TcPO2)	X(4)																
Assessment of re-epithelialization				X	X	X	X	X	X	X	X	X	X	X	X	X (2)	
SF-36 Questionnaire and Pain Scale			X												X (5)		
Randomization			X														
Visual examination of wound(s) and imaging with eKARE inSight	X	X	X	X	X	X	X	X	X	X	X	X	X	X	X	X (2)	
Product application with Restrata			X		X		X		X		X		X		X		
Standard of Care			X	X	X	X	X	X	X	X	X	X	X	X	X		
Adverse events			X	X	X	X	X	X	X	X	X	X	X	X	X	X (2)	X (2)
Telephone follow-up																	X (2)

Notes:

- X – Requirement completed during patient encounter
- (1) – Treatment period visits will cease after 100% re-epithelialization of all study wounds is confirmed.
- (2) – An in-person visit two weeks (± 3 days) after 100% re-epithelialization is first identified, and a telephone call six months (± 1 month) after Week 0 are required for patients with 100% wound re-epithelialization of at least one wound. These visits are NOT required if there is not 100% re-epithelialization of any wound at or before 12 weeks.
- (3) – Weeks 5 and 9 may be conducted virtually at the discretion of the investigator and based on the evaluator’s assessment at Weeks 4 and 8. A visual wound assessment and wound imaging are not required if the visit is virtual. If the patient is randomized to SOC, then SOC would not be applied during a virtual visit (at the physician’s discretion).
- (4) – HbA1c and a vascularization assessment can be completed anytime within 60 days prior to Week 0
- (5) – SF-36 Questionnaire and Pain Scale will be completed during the visit when 100% re-epithelialization of all wounds is first identified or at 12 weeks (whichever occurs first)

5.2 Schedule of Events for Venous Leg Ulcer (VLU) Patients

Requirement	Run-In Period		Treatment Period (1)																Two-Week In-Person Follow-Up (2)	Six-Month Telephone Follow-Up (2)		
	Start	7 days (± 3 days)	Week 0 is the initial application of study product and occurs 14 to 17 days after the start of the run-in period.																2 weeks after each wound closure (± 3 days)	Six-Months After Week 0 (± 1 month)		
			Visit window for Weeks 1 through 16 is (± 3 days)																			
			0	1	2	3	4	5 (3)	6	7	8	9 (3)	10	11	12	13	14	15	16			
Informed consent	X																					
Screening	X	X	X																			
Demographics and history	X																					
HbA1c	X(4)																					
Vascularization (ABI, TBI, TcPO2, or DUS)	X(4)																					
Assessment of re-epithelialization				X	X	X	X	X	X	X	X	X	X	X	X	X	X	X	X	X	X	X
SF-36 Questionnaire and Pain Scale																			X (5)			
Randomization			X																			
Visual examination of wound(s) and imaging with eKARE inSight	X	X	X	X	X	X	X	X	X	X	X	X	X	X	X	X	X	X	X	X	X	X (2)
Product application (for both assignments)			X		X		X		X		X		X		X		X		X			
Adverse events			X	X	X	X	X	X	X	X	X	X	X	X	X	X	X	X	X	X	X	X (2)
Telephone follow-up																						X (2)

Notes:

-
- X – Requirement completed during patient encounter (1) – Treatment period visits will cease after 100% re-epithelialization of all study wounds is confirmed.
- (2) – An in-person visit two weeks (± 3 days) after 100% re-epithelialization is first identified, and a telephone call six months (± 1 month) after Week 0 are required for patients with 100% re-epithelialization of at least one wound. These visits are NOT required if there is not 100% re-epithelialization of any wound at or before 16 weeks.
- (3) – Weeks 5 and 9 may be conducted virtually at the discretion of the investigator and based on the evaluator’s assessment at Weeks 4 and 8. A visual wound assessment and wound imaging are not required if the visit is virtual.
- (4) – HbA1c (for patients with a known history of diabetes) and a vascularization assessment can be completed anytime within 60 days prior to Week 0
- (5) – SF-36 Questionnaire and Pain Scale will be completed during the visit when 100% re-epithelialization of all wounds is first identified or at 16 weeks (whichever occurs first)

5.3 Screening

A patient screening log will be maintained. For patients who do not meet eligibility criteria, the reason(s) for exclusion from the study will be documented.

Patients will undergo the benefit insurance verification process via the third-party Reimbursement Support Hotline prior to or during the run-in period. Product Reimbursement will be confirmed for the comparison product (Apligraf).

5.4 Informed Consent

Prior to the start of the 2-week run-in period and the completion of any non-standard of care study activities, written informed consent shall be obtained from the patient or the patient's legally authorized representative (LAR). The investigator (or designee) must ensure that each patient (or LAR) is fully informed about the nature of the study, study objectives, study products, study procedures, and possible risks and benefits associated with participation in this study. Information shall be provided to the patient (or LAR) in a language and level of complexity so that he/she understands. The patient (or LAR) will have adequate time to consider participation in the study and have the opportunity to ask questions. The patient (or LAR) will sign and date the informed consent form, and he/she shall be provided a signed copy of the form. The investigator (or designee) will retain each patient's original signed informed consent form.

If significant new information is obtained after a patient is enrolled, the patient will be informed about the new information if the patient has not exited the study. Any discussions with the patient about new information should be documented. Patients will sign a new informed consent form at the discretion of the investigator and/or the IRB/EC.

The initial informed consent form and any revisions made during the course of the study must be approved by both the IRB/EC and Acera Surgical, Inc. before use.

5.5 Run-In Period

A 2-week run-in period will be required prior to enrollment/randomization and treatment in order to complete screening assessments and confirm that the wound(s) has not decreased in size by more than 30%. Written informed consent must be obtained prior to or at the beginning of the run-in period.

More than one wound per patient may be screened, enrolled and randomized to a study product. All wounds screened/enrolled must be either DFUs or VLUs. A patient may not have both a DFU and VLU that are screened and randomized to a study product. If more than one wound is enrolled, then the wounds must be at least 3 cm apart. Additionally,

the run-in period will begin on the same day for all wounds. A patient may not have a separate run-in period for each wound.

5.5.1 First Visit of Run-In Period (14 to 17 days before randomization)

An in-person visit will be completed at the beginning of the 2-week run-in period, and the following will be completed:

- Written informed consent will be obtained
- Assessment of inclusion/exclusion criteria
- Collection of demographics and medical history information
- Assessment of HbA1c in patients with known history of diabetes if it was not completed within the previous 42 days
- If vascularization in the study leg(s) was not assessed within the previous 42 days, then at least ONE of the following shall be completed:
 - Ankle-brachial index (ABI) of study leg(s)
 - Toe-brachial index (TBI) of study extremity(ies)
 - TcPO₂ of study leg(s)
 - Doppler waveform of study leg(s) (VLU patients only)
- Assessment of ulcer(s) size via the eKare inSight platform according to the eKare in Sight instructions. If debridement is completed during this visit, then the assessment must be completed after debridement.
- Assessment of wound(s) for signs of infection, wound progression, and tissue healing. Gross observation will be utilized to determine the need for change in dressing type or dressing replacement/change.

NOTE: Informed consent must be obtained prior to the above assessments if they are not considered standard of care at this visit.

If the patient does not continue to meet all inclusion/exclusion criteria by the end of the visit, then they will be considered a screen failure and should not proceed with additional visits/assessments. If a patient has more than one wound that is screened, then wound(s) that do not continue to meet all inclusion/exclusion criteria will not be randomized to a study product.

5.5.2 Second Visit of Run-In Period (7 days ± 3 days After First Visit)

An in-person visit will be completed 7 days after the first run-in visit (± 3 days), and the following will be completed

- Assessment of ulcer(s) size via the eKare inSight platform according to the eKARE in Sight instructions. If debridement is completed during this visit, then the assessment must be completed after debridement.

- Assessment of wound(s) through gross observation and analysis for signs of infection, wound progression, and tissue healing. Gross observation will be utilized to determine the necessity of standard dressing change.
- Continued assessment of inclusion/exclusion criteria.

If the patient does not continue to meet all inclusion/exclusion criteria, then they will be considered a screen failure and should not proceed with additional visits/assessments. If a patient has more than one wound that is screened, then wound(s) that do not continue to meet all inclusion/exclusion criteria will not be randomized to a study product.

5.6 Point of Enrollment

Patients will be considered enrolled after ALL of the following requirements are met:

- Written informed consent is provided
- For patients with a DFU(s), the patient meets all DFU inclusion criteria and no DFU exclusion criteria
- For patients with a VLU(s), the patient meets all VLU inclusion criteria and no VLU exclusion criteria
- The patient has completed the 2-week run-in period with $< 30\%$ reduction in wound(s) size
- The patient is randomized

5.7 Randomization

The randomization process will be pre-programmed into the electronic data capture (EDC system) prior to enrollment of the first study patient.

Once the patient meets all enrollment criteria and has completed the 2-week run-in period, the patient will be randomized. Patients with a DFU(s) will be randomized to receive either synthetic hybrid-scale fiber matrix (treatment group) or SOC (control group). Patients with a VLU(s) will be randomized to receive either synthetic hybrid-scale fiber matrix (treatment group) or living cellular skin substitute (control group).

Randomization will be stratified by wound size:

- DFUs will fall into two groups ($>1.0 \text{ cm}^2$ and $< 12.5 \text{ cm}^2$) and ($\geq 12.5 \text{ cm}^2$ and $< 25 \text{ cm}^2$). Patients within each group will be randomized in a 1:1 ratio to receive either synthetic hybrid-scale fiber matrix or SOC.
- VLUs will fall into two groups: ($>1.0 \text{ cm}^2$ and $< 25 \text{ cm}^2$) and ($\geq 25 \text{ cm}^2$ and $< 50 \text{ cm}^2$). Patients within each group will be randomized in a 1:1 ratio to receive either synthetic hybrid-scale fiber matrix or living cellular skin substitute.

Once the patient is ready to be randomized, the randomization form will be completed by study personnel in the electronic data capture (EDC) system. The randomization assignment will be obtained from the EDC system prior to the initial application of the study product. If a patient has more than one wound that meets all enrollment criteria, then all wounds will be randomized to the same study product. The largest wound that meets enrollment criteria will determine the size stratification for the patient.

Any patients that exit the study before randomization are considered screen failures. A study exit CRF shall be completed if the patient is not eligible for randomization.

5.8 Activities for Research Personnel

The following summarizes activities for research personnel from the time of enrollment/randomization through the remainder of the study. See the Schedule of Events Table for additional details.

- The **Evaluator(s)** will complete the following activities:
 - Informed consent
 - Screening assessments
 - Before randomization: administration of the SF-36 Questionnaire and pain scale
 - Before randomization: obtain images of wound(s) via the eKARE inSight Platform
 - Before randomization: assessment of wound(s) through gross observation and analysis for signs of infection, wound progression, and tissue healing
 - Before randomization: wound care including debridement and dressing changes
- Review of wound image(s) during the treatment period for 100% re-epithelialization
 - At Weeks 4 and 8: specify whether or not the patient is likely to have 100% re-epithelialization within the next week so that the investigator can determine whether Weeks 5 and 9 will be completed virtually or in-person. See Section 5.12 for additional details.
 - Review of wound image(s) at follow-up visit two weeks after 100% re-epithelialization to verify wound closure
- - Obtain randomization assignment
 - After randomization: obtain images of wound(s) via the eKARE inSight Platform
 - After randomization: assessment of wound(s) through gross observation and analysis for signs of infection, wound progression, and tissue healing
 - Initial application and re-application of study product

- After randomization: wound care including debridement and dressing changes
- After randomization: assessment of adverse events and medications
- After randomization: administration of the SF-36 Questionnaire and pain scale
- Virtual visits at Weeks 5 and 9, if conducted
- Telephone call six-months after initial product application to verify wound closure, drainage, and need for additional dressing

5.9 Treatment Week 0

An in-person visit will be completed 14 to 17 days after the beginning of the run-in period.

The following will be completed PRIOR TO randomization:

- Verify that the patient has active insurance.
- Review of the patient's medical history
- Assessment of medications including steroid use
- Assessment of Quality of Life - SF-36
- Pain Scale
- Assessment of wound(s) for signs of infection, wound progression, and tissue healing. Gross observation will be utilized to determine the necessity of standard dressing change.
- After initial debridement, assessment of ulcer size via the eKARE Insight platform according to the eKARE in Sight instructions. Document whether or not the ulcer size has decreased by < 30% since the beginning of the run-in period. If more than one ulcer is screened for the study, then only ulcers that have decreased in size < 30% may be randomized.

After the eKARE Insight assessment is complete, review all inclusion/exclusion criteria to verify the patient is eligible for enrollment and randomization. **Once all criteria is confirmed, the patient will be randomized.** If the patient does not meet all inclusion/exclusion criteria, then the patient will be considered a screen failure, and a study exit CRF shall be completed. If the patient has more than one ulcer that has been screened, ulcers that do not meet all inclusion/exclusion criteria will not be randomized and should receive treatment according to standard of care. All ulcers that meet enrollment criteria will be treated with the same study product beginning on the same day.

Before the patient is randomized, blinded evaluators should leave the area within view of the patient. Study product will then be applied by **study personnel**.

5.9.1 Application of synthetic hybrid-scale fiber matrix

Follow the instructions below for patients receiving synthetic hybrid-scale fiber matrix.

1. Wound Bed Preparation:

- Prepare the wound bed using standard methods to ensure it is free of exudate and devitalized tissue. An initial excision or debridement of the wound is necessary to ensure the wound edges contain viable tissue.
- Wait for any bleeding to stop and ensure there is no active bleeding before applying synthetic hybrid-scale fiber matrix.
- Cleanse the wound thoroughly with sterile saline prior to application of synthetic hybrid-scale fiber matrix.

2. Preparation of synthetic hybrid-scale fiber matrix:

- Select the appropriate size sheet of synthetic hybrid-scale fiber matrix based on the eKARE inSight measurements.
- ***Heavily fenestrate with a scalpel or mesh prior to application.*** Synthetic hybrid-scale fiber matrix must be fenestrated prior to use in any wound prone to exudate in order to permit effective exudate management.
- Synthetic hybrid-scale fiber matrix is packaged in a nested pouch configuration. Peel open the outer foil pouch starting from the chevron sealed edge. The inner TyVek[®] pouch is sterile and may be placed on the sterile field.
- Rinse surgical gloves, if necessary, to remove any glove powder prior to touching the product.
- Synthetic hybrid-scale fiber matrix can be cut to the desired shape in a wet or dry state. In order to increase pliability of the product, hydrate in warm, sterile, hypertonic solution (i.e., saline, water, etc.) for a minimum of 1 minute.

3. Application of synthetic hybrid-scale fiber matrix:

- Apply matrix with either side towards the wound bed, and position to completely contact the entire surface of the wound bed and extend slightly beyond wound margins. The matrix can be repositioned as necessary.
- Securely anchor the matrix as needed with suture or Steristrips.
- Apply a non-adherent primary wound dressing over the matrix.

- To prevent dislodgment of product, apply appropriate secondary dressing or compression to maintain dressing adherence (e.g., multi-layer compression bandage system, or other appropriate dressing), manage the wound exudate, keep the matrix moist, and keep all layers securely in place. The optimum secondary dressing is determined by wound location, size, depth and provider preference.
- Discard any unused pieces of study product.

A non-adherent primary dressing will be applied to the wound bed. Management of wound exudate will determine the required dressing. The dressing will be securely in place and dressing determined by provider preference.

5.9.2 Application of Living Cellular Skin Substitute (VLU Patients Only)

Follow the living cellular skin substitute instructions for use (IFU) in Appendix C for VLU patients randomized to this group. Post-application, cover living cellular skin substitute using a non-adhesive primary dressing. Apply a secondary non-occlusive dressing to create a bolster.

5.9.3 Post-Application Procedures

- Assessment of adverse events
- **For DFUs:** To ensure off-loading, each patient will be fitted with an off-loading device based on the investigator's decision, e.g., a boot for forefoot and a heel protector for hindfoot. Patients should be instructed on how to care for the surgical site, utilize an off-loading device, and keep the surgical site moist and clean. If the wound is dry, a hydrogel category dressing type should be used. If the wound has exudate, an aliginiate or foam dressing is recommended.
- **For VLUs:** Patients will be provided with a compression device. Patients should be instructed on how to care for the surgical site, utilize compression socks and/or compression wrap, e.g., ProFore or a similar product, and keep the surgical site moist, and clean.

5.10 Study Treatment Period - For synthetic hybrid-scale fiber matrix and comparison products

Patients will have weekly visits for up to 12 weeks for patients with DFUs and up to 16 weeks for patients with VLUs (the window for all of these visits is ± 3 days). Assessment and imaging of the wound(s) will occur at each weekly visit unless the visit is conducted virtually (optional for Weeks 5 and 9). Assessment of adverse events and medications will be occur during each weekly visit.

Study product will be re-applied:

- **DFU patients:**
 - **Randomized to Restrata: Biweekly (weeks 2, 4, 6, 8, 10, and 12)**
 - **Randomized to Standard of Care: Weekly**

- **All VLU patients: Biweekly (weeks 2, 4, 6, 8, 10, 12, 14 and 16)**

If 100% re-epithelialization of all study wounds is confirmed before 12 weeks for DFU patients or before 16 weeks for VLU patients, then weekly visits shall cease.

5.10.1 The **evaluator** will complete these assessments at each in-person weekly visit during the Treatment Period:

- Review of images and documentation of 100% re-epithelialization, if present

5.10.2 Personnel will administer the Quality of Life - SF-36 Questionnaire and the pain scale at the following time-point (whichever occurs first):

- When complete wound re-epithelialization of all wounds is first identified, OR
- At Week 12 for DFU patients, OR
- At Week 16 for VLU patients

5.10.3 Personnel will complete the following assessments at each weekly in-person visit:

- Assessment of wound(s) through gross observation and analysis, wound progression, and tissue healing. Gross observation will be utilized to determine the necessity of standard dressing change. Carefully assess the wound(s) for signs of infection, description of exudate present, and wound bed characteristics.
- Assessment of adverse events and medications
- Debridement and dressing changes may occur at each weekly visit or as needed.
 - Debride the wound(s) as needed while not disrupting healing tissue.

- The clinician will inspect the wound bed for signs of infection and healing; the secondary dressing is changed as appropriate with a nontoxic solution. Frequency of secondary dressing changes will be dependent upon the volume of exudate produced, type of dressing used and the clinician's decision upon inspection of the wound(s).
- Measurement and imaging of wound area via the eKare inSight platform according to the eKare inSight instructions. If debridement is completed during this visit, then the assessment must be completed after debridement.

5.10.4 Reapplication of the study product by personnel will occur:

- **DFU patients:**
 - **Randomized to Restrata: Biweekly up to 12 weeks**
 - **Randomized to Standard of Care: Weekly up to 12 weeks**
- **All VLU patients: Biweekly up to 16 weeks**

If 100% re-epithelialization is confirmed before 12 weeks for DFU patients or before 16 weeks for VLU patients, then re-application shall cease. For patients with more than one wound randomized to the study, re-application of product to each wound shall cease when 100% re-epithelialization of that wound is confirmed. The following will be completed by qualified personnel:

- Evaluate the amount of study product remaining in the wound.
- If the study product is completely intact (no resorption has occurred) and the wound is clean and clear of infection, then leave the product in place.
- The study product should be reapplied over previously absorbed material.
- If any of the study product material has resorbed, then evaluate for additional debridement prior to replacement with new study material.
- In the event the material does need to be removed from the wound bed prior to reapplication, use warm (37°C) sterile saline to continuously rinse the wound site to help detach the material, so as not to cause further damage to the wound bed. Forced removal may result in wound re-injury.

NOTE: If excess exudate collects under Synthetic hybrid-scale fiber matrix, the material should be thoroughly fenestrated to allow the exudate to drain.

5.11 3D Wound Measurement with the eKare inSight Platform

Wounds will be measured using the eKare inSight platform weekly from the beginning of the run-in period until 12 weeks for DFU patients or 16 weeks for VLU patients (except Weeks 5 and 9 if conducted virtually). If 100% re-epithelialization of all wounds is confirmed before 12 weeks for DFU patients or before 16 weeks for VLU patients, then

measurements shall cease. Qualified personnel who are trained on the system will be required to complete the assessment. **If debridement is completed at the visit, then the measurement must occur after debridement.**

The inSight platform uses structured light to produce three-dimensional renderings of wounds and translates the data into area, length, width, depth and volume within seconds.

Each investigational site will be provided with one system, which will need to be returned to the Sponsor at study conclusion.

5.12 Virtual Visits at Weeks 5 and 9

Based on the evaluator's assessment of the wound image and at discretion of the investigator, Week 5 and Week 9 may be conducted virtually (via telephone call or web meeting) by un-blinded study personnel. A visual wound assessment and wound imaging via the eKARE inSight platform are not required if the visit is virtual. If a DFU patient was randomized to Standard of Care, then product reapplication is not required if the visit is virtual. The following will be completed during virtual visits:

- Collect information about adverse events and medications
- Collect information about wound drainage and dressing changes since the previous visit
- Discuss wound care recommendations including any needed dressing changes

At Week 4, the **evaluator** will complete an assessment of the wound image and determine whether or not 100% re-epithelialization is likely to occur before Week 5.

- If 100% re-epithelialization of any wound is likely to occur before Week 5 based on the blinded evaluator's assessment, then an in-person visit will be completed at Week 5.
- If 100% wound re-epithelialization is unlikely to occur before Week 5 based on the blinded evaluator's assessment, then the investigator will determine whether Week 5 will be completed virtually or in-person based on the patient's best interest. For DFU patients randomized to Standard of Care, a visit may be conducted virtually only if the investigator determines it is in the patient's best interest to forego product reapplication at Week 5.

At Week 8, the **evaluator** will complete an assessment of the wound image and determine whether or not 100% re-epithelialization is likely to occur before Week 9.

- If 100% re-epithelialization of any wound is likely to occur before Week 9 based on the evaluator's assessment, then an in-person visit will be completed at Week 9.
- If 100% re-epithelialization is unlikely to occur before Week 9 based on the evaluator's assessment, then the investigator will determine whether Week 9 will be completed virtually or in-person based on the patient's best interest. For DFU patients randomized to Standard of Care, a visit may be conducted virtually only if the investigator determines it is in the patient's best interest to forego product reapplication at Week 9.

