
Secondary Outcome Measures
	
 1. Decrease in wound area 2. Time from initial application of study product to 100% re-epithelialization of wound 3. Total number of product applications

Tertiary Outcome Measures
	
 1. Quality of Life - SF-36 Questionnaire 2. Pain reported by patient 3. Incidence of adverse events 4. Ease of Use and handling of study product 5. Cost effectiveness / economic model (amount of product usage, length of treatment) 6. Reimbursement and/or payer access

Assessment Time-Points
	
 ➤ Run-In Period to verify enrollment criteria: 2 weeks before initial application of study product ➤ Product Application: 
 ○ DFUs: 
 ▪ Patients randomized to synthetic hybrid-scale fiber matrix: Biweekly application for either 12 weeks or until 100% re-epithelialization (whichever occurs first) ▪ Patients randomized to Standard of Care: Weekly dressing application for either 12 weeks or until 100% re-epithelialization (whichever occurs first) ○ VLUs: Biweekly application for either 16 weeks or until 100% re-epithelialization (whichever occurs first) ➤ Wound assessment, imaging, and AEs: 
 ○ DFUs: Day of initial product application and weekly for either 12 weeks or until 100% re-epithelialization (whichever occurs first) ○ VLUs: Day of initial product application and weekly for either 16 weeks or until 100% re-epithelialization (whichever occurs first) ➤ Quality of Life and Pain Assessments: 
 ○ DFU patients: Day of initial product application and at either 100% re-epithelialization or 12 weeks (whichever occurs first) ○ VLU patients: Day of initial product application and at either 100% re-epithelialization or 16 weeks (whichever occurs first)

- | | |
|--|--|
| | 
➤ For patients with 100% re-epithelialization:
○ Clinic visit two weeks after 100% re-epithelialization to verify wound closure, drainage, and need for additional dressing○ Telephone call six-months after initial product application to verify wound closure, drainage, and need for additional dressing |
|--|--|

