9.5.5 Secondary Endpoints

The following secondary endpoints will be summarized for exploratory purposes. There are no plans for statistical testing of secondary endpoints.

Decrease in Wound Area from Baseline

The difference in wound area from baseline to each time point will be summarized for each treatment group in each arm. The difference in mean percent change in size between the treatment group and control group will be calculated for each timepoint. Wound area measurements will be made via the eKARE inSight system every week (except during virtual visits) for 12 weeks for DFU patients and 16 weeks for VLU patients (except during virtual visits), or until 100% re-epithelialization, whichever occurs first.

Time to Wound Closure

The time to wound closure will be summarized by proportion of patients with wound closure at each timepoint for each treatment group in each arm. The difference in proportion of patients with wound closure between the treatment group and control group will be calculated for each timepoint. Persistence of wound closure will be verified via confirmatory visit within 2 weeks after complete closure has been first determined.

Number of Product Applications

The number of product applications will be summarized for each treatment group in each arm. The difference in mean number of applications between the treatment group and control group will be calculated for each timepoint. Product applications will be defined as the number of product applications prior to complete wound closure within the treatment period for each study arm.

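### Weekly wound area, the first-listed secondary outcome, is measured by staff who know the assignment, although the blinded evaluator already reviews the same images

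*Combined protocol and SAP*

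**What the plan says.** **The outcome.** The Protocol Summary (Section 1) lists "1. Decrease in wound area" at the head of the secondary outcomes. Section 9.5.5 plans its comparison: "The difference in mean percent change in size between the treatment group and control group will be calculated for each timepoint". The same section says that the secondary endpoints are exploratory and will not be tested.

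**Who does what.** Section 5.8 contains two lists of tasks.
- The first belongs to the evaluator and includes "Before randomization: obtain images of wound(s) via the eKARE inSight Platform". After randomization the evaluator's tasks are confined to reviewing images for closure, judging at Weeks 4 and 8 whether closure is near, and verifying closure two weeks later.
- The second list has no heading in the text available. It includes "Obtain randomization assignment", "Initial application and re-application of study product" and "After randomization: obtain images of wound(s) via the eKARE inSight Platform", as well as debridement and the virtual visits.

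**Weekly visits.** Section 5.10.1 gives the evaluator "Review of images and documentation of 100% re-epithelialization, if present". Section 5.10.3 gives personnel, listed separately, the item "Measurement and imaging of wound area via the eKare inSight platform according to the eKare inSight instructions".

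**Blinding and the device.** Section 3 has the blinded evaluator assess re-epithelialization for the primary outcome through the eKARE platform. For wound area it names the platform but no blinded reader. Section 5.9 has blinded evaluators withdraw before randomization. Section 5.11 asks that the measurer be trained on the system, and says that the platform uses structured light and returns area within seconds.

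**The concern.** The plan treats knowledge of the assignment as a risk to the closure reading and protects that reading with a separate, blinded evaluator. It does not extend this protection to wound area, although the evaluator opens the very images from which area is derived.

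If the person at the device has any say in where the wound edge lies, knowledge of the assignment can move that edge differently in the two groups. The shift would appear as a product effect at every week in the 9.5.5 summary. It is systematic error, so neither the planned sample nor an increase after the interim analysis would reduce it. Section 2.2 names decrease in wound size among the outcomes the study is meant to give to payers, so the figure is likely to be read even though it is not tested.

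**Working it through.** The plan states no figure on this point, so the main check is to set the role assignments side by side.

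**Step 1: is the weekly measurer aware of the assignment?** The inference rests on two things. The second list in 5.8 holds both obtaining the assignment and applying the product, so that role cannot be blind. The same list holds the virtual visits, which 5.12 gives to un-blinded staff. Section 5.10.3 then gives area measurement to personnel who are distinguished from the evaluator of 5.10.1. The missing list heading leaves this as an inference, but the tasks allow no other reading.

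**Step 2: does any blinded person measure area after randomization?** Sections 3, 5.8, 5.10, 5.11, 5.12 and 9.5.5 do not provide for it. The evaluator's post-randomization review concerns closure only.

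**Step 3: how large could the bias be?** Let R be the fraction of baseline area truly remaining, equal in both groups, and let b be the relative amount by which area is read too small in the matrix group only. The measured percent change in that group is 100 × [R(1 − b) − 1], against 100 × (R − 1) in the control group. The spurious difference is 100 × b × R percentage points in favour of matrix. Both b and R are assumptions; neither is in the documents.

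| R | b = 5% | b = 10% |
|---|---|---|
| 0.3 | 1.5 | 3.0 |
| 0.5 | 2.5 | 5.0 |
| 0.7 | 3.5 | 7.0 |

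With b = 0, as under a fully automatic border, every entry is zero.

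**Step 4: does the change of observer after baseline matter?** Baseline is taken before anyone knows the assignment. Suppose the later observer reads every wound larger by a relative amount s, in both groups. The extra difference is 100 × s × (R1 − R2). With R1 = R2 = 0.3 it is zero. With R1 = 0.2, R2 = 0.4 and s = 10%, its size is 100 × 0.10 × 0.2 = 2 points, on a true difference of 20. A common shift rescales a real difference slightly but cannot create one.

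**Step 5: how many images are involved?** With one wound per patient and no early closure or virtual visit:
- planned size: 12 × 110 + 16 × 60 = 1,320 + 960 = 2,280;
- maximum size: 12 × 166 + 16 × 90 = 1,992 + 1,440 = 3,432.

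Patients may have more than one enrolled wound (5.5, 5.7), which would raise these counts. Closures and virtual visits at Weeks 5 and 9 would lower them.

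**The case against.** **The device is objective.** Structured light yields area within seconds, measurement must follow the device instructions, and no passage describes anyone drawing an outline. Training is consistent with simple image capture. This stands in part: operator influence is not shown, and the device instructions are not in the documents. It is not excluded either. The matrix is placed to reach slightly past the wound margin (5.9.1) and intact product is left in place (5.10.4), so finding the edge may call for judgement. In the DFU comparison only one group has such product. That is inference, and it is enough only to say that automation cannot be presumed.

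**The outcome is exploratory.** This stands. No p-value or success criterion depends on area, which limits the weight of the point. The difference is still planned at every timepoint.

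**The direction is unknown.** This also stands, most clearly for VLU, where the comparator is itself a marketed skin substitute. The table in the working shows one direction only as an illustration.

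**Two stronger readings are tempting.** A reader might infer that having the evaluator image at baseline and other staff afterwards is itself a source of bias. It is not a source of differential bias, because the change of observer is the same in both groups. A reader might also infer that the primary endpoint shares the defect. The documents do not support that: its re-epithelialization component is read by the blinded evaluator, although from images that un-blinded staff capture.

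**Conclusion.** The point holds in a limited form. After randomization, area is measured by staff who know the assignment, no blinded reading of area is planned, and 9.5.5 nevertheless compares the groups on it each week. The comparison is open to observer bias to the extent that the operator affects the border.

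The size cannot be determined from the documents. It is nil from outlining if the border is automatic, and 1.5 to 7.0 points over the assumed ranges of b (5% to 10%) and R (0.3 to 0.7). Those figures show scale only and are not evidence that such an error occurs. The conclusion rests on reading the unheaded list in 5.8 as the treating, un-blinded role. Because the outcome is exploratory and untested, this is an inexpensive improvement worth making and does not threaten the trial's main conclusion.

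**What to change.** - **Sections 5.8, 5.10.1 and 5.10.3:** treating staff capture the image; the blinded evaluator sets or accepts the wound border on the weekly image already reviewed for closure.
- **Section 9.5.5:** state that the evaluator's area is the analysis value, and that any on-site reading by treating staff is not used for analysis. This also settles which of two readings from one visit counts.
- **Alternative:** if the platform sets the border without operator input, say so in 5.11. The outlining concern then falls away and no change of roles is needed.

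**Cost.** Protocol wording and some evaluator time per image, on about 2,280 images at the planned size and about 3,432 at the maximum sizes with one wound per patient, and more with multiple wounds. No extra staff are needed, since 5.10.1 already requires image review at each in-person visit. The change depends on the platform allowing the border to be set or accepted on a stored image, which the documents do not confirm.

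**What remains.** The change reduces the bias but does not remove it. Un-blinded staff would still debride before the measurement and capture the image, and product visible in the wound could reveal the assignment to the evaluator.
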